9.1.3 Expression of WASP

Presence of detectable WASP expression (lymphocytes, T Cells, B Cells NK cells, monocytes, platelets) at 1 year after gene therapy by flow cytometry analyses and/or Western Blot.

WASP expression data assessed by flow cytometry will be summarised with descriptive statistics including 95% CI. The mean change from baseline will be calculated with 95% CI. The longitudinal profile over time of WASP expression will be described with a listing for qualitative results from Western Blot if available; and a figure for quantitative results from flow cytometry.

A line plot will be created for median WASP expression values over time. Also a plot of the arithmetic mean WASP expression values with 95% CI over time will be created.

9.1.4 T-cell function

T-cell function is evaluated as part of immunological evaluation: dose response of proliferation to anti-CD3i after anti-CD3i mAb stimulation *in vitro*. Change from baseline in T-cell proliferation upon stimulation with anti-CD3i mAbs will be calculated for each year after OTL-103 administration of gene therapy.

Summary statistics of the absolute values and change from baseline will be calculated along with 95% CI for the mean by level of anti-CD3i stimulation for cells per minute (CPM) and simulation index (SI) separately. A boxplot comparing T-cell function at each year post gene therapy versus baseline will be produced by anti-CD3i levels.

The longitudinal profile over time of the levels of the *in vitro* T-cell proliferation will be described by means of a listing (including observed and change from baseline values) and a plot.

Plots will also be created for the absolute values and change from baseline means and 95% confidence interval of T-Cell proliferation responses over time.

Scatterplots will be presented of treatment dose (CD34+/kg), busulfan dose (AUC), and age at treatment against T-cell response (at 0.01, 0.1 and 1 ug/mL for both SI and CPM) at each year post gene therapy.

A listing will be created for the results from the TCR repertoire results.

9.1.5 Antigen-specific responses to vaccination;

Antigen-specific responses to vaccinations are measured in three ways:

- a. Ability to mount a protective humoral response to nominal antigens, including antibodies to at least 4 out of 5 T cell dependent antigens tested (antibodies against Tetanus Toxoid, Diphtheria, Hepatitis B, Pertussis, Haemophilus measured after the end of the vaccination schedule (foreseen >1 year after gene therapy). In case results are available on n<5 antigens, the rule of at least n-1 will be applied for defining success. If there is only 1 available result and this is a protective response, this will also be considered a success.
- b. Ability to mount a protective humoral response to unconjugated polysaccharide antigens (Pneumococcus either IgG or IgM), measured after the end of the vaccination schedule (foreseen >1 year after gene therapy).
- c. Positive cellular response to Tetanus Toxoid after vaccination, measured by in vitro proliferative response >1 year after gene therapy.

Response to vaccination will only be looked at in subjects who have completed the required schedule for the specific vaccination and have had a period of at least 90 days after their last IVIG infusion.

Reference values to define protective or positive responses are summarised below for each specific antigen.

Table 6 Reference values for protective response by antigen

Parameter	Protective response cut-off	Unit
Tetanus Toxoid	820	cpm
Tetanus IgG	0.4	IU/mL
Pneumococcus IgG	200	titre
Pneumococcus IgM	100	titre
Pertussis IgG Antibody	11	Arbitrary U
Hepatitis B Virus Surface Antibody	100	mU/mL
Hemophilus influenzae B Antibody	1	mg/L
Diphtheria IgG Antibody	0.4	IU/mL

A summary of response at any point within the first 3 years after GT as well as over the whole follow-up phase will be produced. In addition, the longitudinal profiles over time of responses to vaccinations will be described together with vaccinations in a listing.

A summary of the number of IVIG infusions per treatment phase will be presented along with the rate of infusions per year of observation.

A summary of time to sustained IVIG discontinuation will be produced for subjects who no longer need IVIG infusions. The cessation of sustained IVIG treatment is defined as a period of 3 months post gene therapy without IVIG treatment. The time to discontinuation will be presented in a table and Kaplan Meier plot including median time to discontinuation and 95% confidence interval.

Separate listings will be produced for patients requiring IVIG infusions and time to IVIG discontinuation (for those subjects who no longer need IVIG infusions).

9.1.6 Platelet counts and Mean Platelet Volume.

Absolute values of platelet count and mean platelet volume (MPV) as well as change from baseline will be calculated according to the planned follow up visits and including platelet count collected for clinical reasons during follow up (in infusion independent subjects). Baseline platelet count will be calculated as the median of the (at least three) determinations performed before beginning of treatment.

Normalization of MPV is defined as MPV within the normal range (MPV \geq 7.4 fL for children (< 18 years) and MPV \geq 9.1 fL for adults). Platelet count data obtained within 7 days following platelet infusions will not be considered for evaluation.

Subjects will be also stratified according to the severity of thrombocytopenia before gene therapy in 5 groups (A, B, C, D and E) and the subject will be defined as improved if there is a positive shift (an increase in platelet count) from one group to the subsequent as shown in Table 7. If a subject has no values more than 7 days from a platelet infusion then they are imputed as being in group A.

Table 7 Stratification of platelet count according to severity of thrombocytopenia (count $\times 10^9/L$)

A	B	C	D	E
< 20	20 - < 50	50 - < 100	100 - < 150	≥ 150

The percentage of subjects who have improved platelet count over baseline at 1 to 8 years (annually) after gene therapy will be calculated with 95% CI.

The means for absolute values and change from baseline will be calculated with 95% CI each year after gene therapy for platelet count and MPV. There will also be accompanying summary statistics.

At 1-8 years after gene therapy the number of subjects with normal MPV will be summarised. The longitudinal profile over time of platelet count and MPV will be described by means of a listing and a plot. The listing will identify which platelet count data points were within 7 days after a platelet infusion as well as thrombocytopenia severity data.

Shift tables of platelet count (as in Table 7) and MPV compared to baseline will be presented for each year after gene therapy.

Median platelet counts will be summarised by baseline WASP expression (Reduced, Absent, Presence of Revertant (>5%)) by means of a bar graph at each year post gene therapy.

Arithmetic mean (and 95% confidence interval) values of platelet count and MPV data will be plotted over time.

A summary of the number of subjects with platelet infusions per treatment phase (See Table 3) will be presented along with the rate of infusions per year of observation.

A summary of time to discontinuation of sustained platelet infusions will be produced for subjects who no longer need platelet infusions. The cessation of sustained infusions is defined as a period of 3 months post gene therapy without a platelet infusion. The time to discontinuation will be presented in a table and Kaplan Meier plot including median time to discontinuation and 95% confidence interval.

Listings of both platelet infusions and time to platelet infusion discontinuation will also be created.

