12.4. Efficacy endpoints

Primary efficacy endpoints

Overall survival

The Kaplan-Meier estimate of survival at 3 years from gene therapy will be obtained, with 95% Confidence Intervals, based on deaths by any causes related to disease. Survival will be also monitored as part of the long-term follow up.

Sustained engraftment of genetically corrected haematopoietic stem cells in peripheral blood and/or in bone marrow

The percentage of subjects who present at one year after gene therapy with adequate engraftment defined as $\geq 4\%$ CD34+ in the bone marrow or $\geq 10\%$ in peripheral blood T lymphocytes will be estimated and the 95% Confidence Intervals (CI) of this proportion will also be calculated. The description of the longitudinal profile over time of the percentage of gene corrected cells on both bone marrow and peripheral blood might be included as additional information.

Expression of vector-derived WASP

The percentage of subjects who present at one year after gene therapy with detectable vector-derived WASP expression will be estimated, with 95% CI.

Improved T-cell functions

The mean change between the pre-gene therapy and the 1-year values of in vitro T-cell proliferation upon stimulation with anti-CD3i will be calculated, with 95% CI, if appropriate. The description of the longitudinal profile over time of the levels of the in vitro T-cell proliferation might be included as additional information. The degree of correction (reached at 1, 2 and 3 years from gene therapy) with respect to normal control levels will also be described.

Antigen-specific responses to vaccinations

The percentage of subjects who respond to vaccination (see Section 9.4) performed > 1 year after gene therapy will be estimated, with 95% CI.

Improved platelet count

The percentage of subjects who improved the level of platelet count at 1, 2 and 3 years after gene therapy compared to baseline, shifting from one category to the subsequent as defined in Section 9.5, will be estimated, with 95% CI. The relative mean change in platelet count with respect to pre-gene therapy value will also be given. The description of the longitudinal profile over time of the platelet count might be included as additional information.

Secondary efficacy endpoints

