Severe infections and bleeding events will be classified according to the time of occurrence relative to treatment as in the Table 3 below. This classification will be used in displays containing severe infections and bleeding events data only. For AE displays including severe infections and bleeding events, the treatment phases for AE data defined in Table 2 will be followed.

Table 3 Windowing for treatment phases; Severe Infections, Bleeding Events and hospitalisations

Assigned Study Day (Inclusive)		Visit Assigned
From	To	
-365	-1	Pre-treatment
2	183	0-6 months follow-up
184	366	6-12 months follow-up
367	731	1-2 Years Follow-up
732	1097	2-3 Years Follow-up
1098	2923	3-8 Years Follow-up
2924	End of study	>8 Years Follow-up
184	End of study	> 6 months Follow-up

Windowing will be applied to the data prior to any missing data calculations.

6 Sample Size

Given the low frequency of disease and the degree of novelty of the proposed experimental approach, we plan to treat overall 8 patients, in an estimated 5-year period.

7 General Considerations

All study patients will be included for evaluation until the earliest time point of the following: completion of a minimum of 5 years follow up in this study (TIGET-WAS) and transition to a separate OLTFU study, death, withdrawal or loss to follow up. Patients who, at 1 year after gene therapy, show absence of transduced cell engraftment in peripheral blood and bone marrow will be subsequently evaluated for safety aspects only.

At the end of the study, when all subjects have completed a minimum of 5 years follow up and transitioned to a separate OLTFU study, a final statistical analysis will be performed with all data available up to the transition to the OLTFU study, and a final clinical study report will be compiled.

The final analyses will be performed after all required database cleaning activities have been completed and final database freeze and database release has been declared by Data Management (DM).

The default significance level will be 5%; confidence intervals will be 95% and all tests will be two-sided. As this study is not powered all p-values and confidence intervals will be nominal.

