7.3 Missing Data

Considering the small sample size of the study, missing data will not be imputed unless otherwise indicated. Missing data will be reported as follows:

- These data will be indicated using a “blank” in subject listing displays. Unless all data for a specific visit are missing in which case the data are excluded from the table.
- Answers such as “Not applicable” and “Not evaluable” are not considered to be missing data and will be displayed as such.

For the evaluation of sustained engraftment, if data on peripheral blood (PB) CD3+ is not available, the missing CD3+ value will be imputed as the average of PB CD4+ and CD8+ values obtained from the same sample at that visit.

Completely missing start or end dates will remain missing, with no imputation applied. Consequently, time to onset and duration of such events will be missing. Partial dates will be displayed as captured in subject listing displays.

Partial dates for adverse events, medical history or concomitant medications records will be imputed for the purpose of assigning phase of onset and in the calculation of duration of adverse events.

The methods for dealing with partial start and stop dates are described below for adverse events and concomitant medications.

The answers to the question “Ongoing?” as recorded on the eCRF pages will also be taken into consideration to determine if the event continued post- gene therapy.

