9.1 Primary Efficacy

The primary efficacy analyses will be based on the ITT population, unless otherwise specified. Table 5 provides an overview of the planned efficacy analyses.

Table 5 Overview of Planned Primary Efficacy Analyses

Endpoint/Parameter/ Display Type	Absolute						Change from Baseline						
	Stats Analysis		Summary		Individual		Stats Analysis		Summary		Individual		
	T	F	T	F	F	L	T	F	L	T	F	F	L
Overall Survival	X	X				X							
Engraftment (PCR for transduced cells)			X	X	X	X							
WASP Expression			X	X	X	X				X			X
T-Cell function			X	X	X	X				X	X		X
Antigen specific response to vaccinations			X	X		X							
Platelet count, MPV			X	X	X	X				X			X

T = Table, F = Figure, L = Listing

Stats Analysis = Represents TFL related to any formal statistical analyses (i.e. modelling) conducted.

Summary = Represents TF related to any summaries (i.e. descriptive statistics) of the observed raw data.

Individual = Represents FL related to any displays of individual subject observed raw data.

Absolute and change from baseline summaries/listings are combined into a single display.

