16.2 Efficacy

16.2.1 Tables

Number	Title	Analysis Set
14.2.1.1.1	Summary of Overall Survival	ITT
14.2.1.2.1	Summary of Subjects with Adequate Engraftment Findings Over Time - Bone Marrow CD34+ and Periperal Blood CD3+	ITT
14.2.1.2.2	Summary Statistics of Vector Copy Number Evaluation in BM and PB cells	ITT
14.2.1.2.6	Summary Statistics of Percentage of Lentiviral Vector Transduced-Colony Forming Units in Bone Marrow Cells (%LVV+ CFU in BM) Over Time	ITT
14.2.1.2.12	Summary of Time to Adequate Engraftment	ITT
14.2.1.3.1	Summary Statistics of Cells Expressing WASP Assessed by Flow Cytometry Over Time	ITT
14.2.1.4.1	Summary Statistics of T-Cell Function	ITT
14.2.1.5.1	Summary of Subjects with Positive Antigen-Specific Responses to Vaccinations	ITT
14.2.1.5.2	Summary of Number and Rate of IVIG Treatment Required by Treatment Phase	ITT
14.2.1.5.3	Summary of Time to Cessation of Sustained IVIG Therapy	ITT
14.2.1.6.1	Summary of Subjects with Improved Platelet Count Over Baseline at Each Year Post Gene Therapy	ITT
14.2.1.6.2	Summary Statistics of Platelet Count and MPV Data	ITT
14.2.1.6.3	Summary of Shifts in Categorical Platelet Count Data From Baseline to Each Year Post Gene Therapy	ITT
14.2.1.6.4	Summary of Shifts in MPV From Baseline to Each Year Post Gene Therapy	ITT
14.2.1.6.7	Summary of Number and Rate of Platelet Infusions by Treatment Phase	ITT
14.2.1.6.8	Summary of Time to Cessation of Sustained Platelet Infusion Therapy	ITT
14.2.2.1.1	Summary of Subjects with Adequate Multilineage Engraftment Findings at Each Year Post Gene Therapy	ITT
14.2.2.2.1	Summary of Severe Infections and All Bleeding Events	ITT
14.2.2.2.3	Summary of Number and Rate of Bleeding Events by Treatment Phase and Severity	ITT
14.2.2.2.4	Summary of Number and Rate of Severe Infections Events by Treatment Phase	ITT

14.2.2.2.6	Summary of Number and Rate of Bleeding Events (Defined from Haemorrhages (SMQ)) by Treatment Phase and Severity	ITT
14.2.2.3.1	Summary of Number of Subjects with Positive Autoimmunity Test	ITT
14.2.2.4.1	Eczema Score Shift Table	ITT
14.2.2.5.1	Summary of Social Life Data Over Time	ITT
14.2.2.5.2	Summary Statistics of Lansky/Karnofsky Performance Index	ITT
14.2.2.6.1	Summary of Days and Rate of Hospitalisation by Treatment Phase	ITT
14.2.3.1.1	Summary of Antimicrobial Treatments by ATC Level 1, Preferred Term and Treatment Phase	ITT
14.2.3.1.2	Summary of Number and Rate of Antimicrobial Treatment Required by Treatment Phase	ITT

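### The vaccination-response rate appears to cover evaluable patients only, and becoming evaluable depends partly on immune recovery, so it can overstate the share of treated patients who responded

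*SAP*

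**What the plan says.** Antigen-specific response to vaccination is a primary efficacy endpoint (Protocol 4.3.1 e). For its analysis, Protocol 12.4 announces "The percentage of subjects who respond to vaccination", for vaccination performed more than 1 year after gene therapy, with a 95% CI. It does not spell out the denominator.

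SAP 9.1.5 sets two conditions for entering the analysis. The first is "Response to vaccination will only be looked at in subjects who have completed the required schedule for the specific vaccination". The second is that patients "have had a period of at least 90 days after their last IVIG infusion". The planned output is "A summary of response at any point within the first 3 years after GT as well as over the whole follow-up phase".

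Four other SAP provisions bear on the denominator:

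- SAP 9.1: "The primary efficacy analyses will be based on the ITT population, unless otherwise specified".
- SAP 7.3: "Considering the small sample size of the study, missing data will not be imputed unless otherwise indicated".
- SAP 16.2.1: Table 14.2.1.5.1, "Summary of Subjects with Positive Antigen-Specific Responses to Vaccinations", carries the label ITT. SAP Table 4 defines ITT as the treated patients with data in the clinical database.
- SAP 7: patients who at 1 year "show absence of transduced cell engraftment in peripheral blood and bone marrow will be subsequently evaluated for safety aspects only".

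Two protocol sections govern who gets vaccinated. Protocol 7.2 (Immunology n°5) starts the vaccination programme in patients who have discontinued IVIG. Protocol 6.11 lists what is weighed in stopping IVIG: IgG troughs holding at 5 g/L or more, no sign of infection, enough circulating B cells, and other risk factors such as season.

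**The concern.** SAP 9.1.5 specifies a restriction, SAP 9.1 gives way to such specifications, and SAP 7.3 imputes nothing by default. Read together, they point to responders divided by evaluable patients. The ITT label on Table 14.2.1.5.1 points to responders divided by all treated patients. A programmer could defend either.

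The choice matters because being evaluable is a state reached after treatment and is probably related to the outcome. A patient whose B cells and IgG do not recover may stay on IVIG, not be vaccinated, and so never count as a non-responder. A patient without engraftment at 1 year moves to safety-only evaluation before an endpoint that is foreseen after 1 year. Both routes can remove likely non-responders from the rate.

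This endpoint is the in vivo part of the primary immune-function objective. A rate confined to the better-recovered patients, in a table labelled ITT, would be read as describing everyone treated.

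**Working it through.** **Inputs.** Planned number treated: 8 (SAP 6). Intervals: 95%, two-sided, nominal (SAP 7), by the Wilson method (Protocol 12.5, SAP 9). The documents give no expected response rate, no number evaluable and no power calculation for this endpoint, so there is no figure of the plan to reproduce. The numbers evaluable (m) and responding (r) below are assumptions. All 8 treated patients are assumed to be in the ITT set.

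**Formulas.**

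- Evaluable-only rate: r/m
- Demonstrated response among all treated: r/8
- Gap: r/m − r/8 = r(8 − m)/(8m). It is zero only if m = 8 or r = 0, and positive otherwise.
- Range for the true share of treated patients, since the outcome of the 8 − m others is unknown: r/8 to (r + 8 − m)/8
- Wilson limits for p = k/n: [p + z²/(2n) ± z·√(p(1 − p)/n + z²/(4n²))] / (1 + z²/n), with z = 1.96

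**One case in full: m = 6, r = 5.**

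- Evaluable only: p = 5/6 = 0.8333. Centre = (0.8333 + 0.3201)/1.6403 = 0.7032. Half-width = 1.96 × √(0.02315 + 0.02668)/1.6403 = 0.2667. Limits 43.6% to 97.0%.
- All treated: p = 5/8 = 0.625. Centre = (0.625 + 0.2401)/1.4802 = 0.5844. Half-width = 1.96 × √(0.02930 + 0.01501)/1.4802 = 0.2787. Limits 30.6% to 86.3%.
- Gap: 5 × 2/(8 × 6) = 20.8 points.
- Range for the true share: 5/8 = 62.5% to 7/8 = 87.5%.

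**Other assumed cases.**

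| Evaluable m | Responders r | r/m, % (95% CI) | r/8, % (95% CI) | Gap, points |
|---|---|---|---|---|
| 8 | 8 | 100 (67.6–100) | 100 (67.6–100) | 0 |
| 7 | 7 | 100 (64.6–100) | 87.5 (52.9–97.8) | 12.5 |
| 7 | 6 | 85.7 (48.7–97.4) | 75.0 (40.9–92.9) | 10.7 |
| 6 | 6 | 100 (61.0–100) | 75.0 (40.9–92.9) | 25.0 |
| 6 | 5 | 83.3 (43.6–97.0) | 62.5 (30.6–86.3) | 20.8 |
| 6 | 4 | 66.7 (30.0–90.3) | 50.0 (21.5–78.5) | 16.7 |
| 5 | 5 | 100 (56.6–100) | 62.5 (30.6–86.3) | 37.5 |
| 5 | 4 | 80.0 (37.6–96.4) | 50.0 (21.5–78.5) | 30.0 |

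**How the SAP treats similar patients elsewhere.** Its other primary endpoints do not supply a rule by analogy. In SAP 9.1.2, engraftment that cannot be determined is set to missing. In SAP 9.1.6, a patient with no platelet count more than 7 days from an infusion stays in the analysis, in the lowest group (A). SAP 9.1.5 has no corresponding sentence.

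**The case against.** The strongest reply is that no passage states an evaluable-only denominator. The restriction in SAP 9.1.5 can be read as a rule about valid measurement, because antibody titres under IVIG cannot be interpreted. The explicit label on the table is ITT, and the shells document mentioned in SAP 8, which I have not seen, may settle the matter. SAP 7.3 also says that recorded answers of not applicable or not evaluable are displayed rather than treated as missing, which weakens the inference that these patients drop out. Protocol 12.4 itself refers to vaccination already performed, so it too can be read as conditional on vaccination. All of this stands as a reason to call the denominator unstated rather than wrong. It does not remove the bias if the SAP text is followed as written.

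Second, IVIG dependence is already reported. Tables 14.2.1.5.2 and 14.2.1.5.3 cover IVIG use and time to cessation, SAP 5.3.4 shows patients still on IVIG as ongoing, and Listings 16.2.6.7, 16.2.6.8 and 16.2.6.21 allow each patient to be followed. A careful reader could work out r/8. But none of these puts all treated patients into the reported rate.

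Third, the safety-only rule might seem to bar non-engrafted patients from an efficacy percentage. Counting them in the denominator as not having shown a response requires no further efficacy assessment of them.

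Fourth, IVIG may continue for reasons such as season, and response counts at any point in the period, so late recoverers can still qualify. Remaining on IVIG is therefore not proof of failure. That is right, and it is why the all-treated figure should be presented as a lower bound.

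Finally, the analyses are descriptive and nominal, and no decision rule uses this percentage. That limits the consequences but does not make the rate easier to interpret.

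**Conclusion.** The concern holds. As written, SAP 9.1.5 leans towards a rate among evaluable patients, and entry to that group depends partly on the recovery the endpoint is meant to show. Such a rate cannot be lower than the share of treated patients with a demonstrated response, and it is higher whenever someone responds and fewer than 8 are evaluable.

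The size is unknown. It is zero if all 8 are evaluable; in the assumed cases with 5 to 7 evaluable it runs from 10.7 to 37.5 points. The link between evaluability and recovery is an inference from Protocol 6.11 and 7.2: well grounded, but not quantified. The 90-day IVIG-free condition is sound; only the denominator and its labelling need attention. I would make the change before the final analysis. My confidence is moderate, because the shells may already state the denominator.

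**What to change.** Keep the 90-day condition and the existing success rule (at least n − 1 antigens when fewer than five results are available). In SAP 9.1.5, for each of the three components and for each planned period (first 3 years, whole follow-up), specify two rates side by side with Wilson 95% CIs:

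1. Responders over evaluable patients, labelled as such.
2. Patients with a demonstrated response over all treated (ITT) patients. Those not evaluable (still on IVIG, unvaccinated, schedule incomplete, no engraftment at 1 year, died or withdrew) are classed as response not demonstrated rather than failed. Show their number and reasons.

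Because eligibility is set vaccine by vaccine, define evaluable for component (a) as having at least one eligible antigen result. Show how many results each patient contributed, so that success under the n − 1 rule can be judged when n is small.

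The cost is a few sentences in SAP 9.1.5 and, if not already present, one row and a footnote in the shell for Table 14.2.1.5.1. It needs no new data and no change to the success rule or to patient care. The drawback is a second, lower percentage in which some patients kept on IVIG for unrelated reasons count as not having shown a response. The listed reasons make that visible.
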